9.5.3 Appropriateness of Measurements

All clinical assessments were standard measurements commonly used in studies of malignant lymphoma.

The safety assessments to be performed in this study, including hematology analyses, blood chemistry tests, urinalysis, vital signs, body weight, ECGs, ECOG-PS, physical examinations, and assessment of AEs, are standard evaluations to ensure subject safety.

9.5.4 Reporting of Serious Adverse Events, Pregnancy, and Events Associated with Special Situations

9.5.4.1 Reporting of Serious Adverse Events

All SAEs, regardless of their relationship to study treatment, must be reported to the sponsor as soon as possible but no later than 1 business day from the date the investigator becomes aware of the event. Completed SAE reports will be sent to the sponsor directly or by fax within 3 business days for fatal or life-threatening AEs and within 5 business days for other SAEs. The faxed report should be followed up by the original SAE report.

SAEs, regardless of causality assessment, must be collected through the final observation visit. All SAEs must be followed to resolution or, if resolution is unlikely, to stabilization. Any SAE judged by the investigator or subinvestigator to be related to the study treatment or any protocol-required procedure should be reported to the sponsor regardless of the length of time that has passed since study completion. For subjects who withdraw from the study and continuously take commercial tazemetostat, all SAEs will be followed until discontinuation visit.

The detailed contact information for reporting of SAEs is provided in the Attachment separately provided to each site.

It is very important that the SAE report form be filled out as completely as possible at the time of the initial report. This includes the investigator's assessment of causality.

Any follow-up information received on SAEs should be forwarded to the sponsor within 1 business day of its receipt. If the follow-up information changes the investigator's assessment of causality, this should also be noted on the follow-up SAE form.

Preliminary SAE reports should be followed as soon as possible by detailed descriptions including copies of hospital case reports, autopsy reports, and other documents if requested by the sponsor.

9.5.4.2 Reporting of Pregnancy and Exposure to Study Drug Through Breastfeeding

Any pregnancy in which the estimated date of conception is either before the last visit or within 30 days of last study treatment, any partner's pregnancy of male subjects in which the estimated date of conception is either before the last visit or within 90 days of last study

Eisai Confidential Page 54 of 71 FINAL: 29 Jan 2021

1 11 VIE. 29 Juli 202

treatment, or any exposure to study drug through breastfeeding during study treatment or within 30 days of last study treatment, must be reported. However, any pregnancy in which the estimated conception is after using commercial tazemetostat is not required to report, as these events are separately collected as spontaneous report.

If an adverse outcome of a pregnancy is suspected to be related to study drug exposure, this should be reported regardless of the length of time that has passed since the exposure to study treatment.

A congenital anomaly, death during perinatal period, an induced abortion, or a spontaneous abortion are considered to be an SAE and should be reported in the same time frame and in the same format as all other SAEs (see Reporting of Serious Adverse Events [Section 9.5.4.1]).

Pregnancies or exposure to study drug through breastfeeding must be reported to the sponsor by fax or email as soon as possible but no later than 1 business day from the date the investigator becomes aware of the pregnancy or breastfeeding. The contact information for the reporting of pregnancies and exposure to study drug through breastfeeding is provided in the Attachment separately provided to each site. The Pregnancy Report Form must be used for reporting. All pregnancies must be followed to outcome. The outcome of the pregnancy must be reported to the sponsor as soon as possible but no later than 1 business day from the date the investigator becomes aware of the outcome.

A subject who becomes pregnant must be withdrawn from the study.

9.5.4.3 Reporting of Events Associated with Special Situations

9.5.4.3.1 REPORTING OF ADVERSE EVENTS ASSOCIATED WITH STUDY DRUG OVERDOSE, MISUSE, ABUSE, OR MEDICATION ERROR

Adverse events associated with study drug overdose, misuse, abuse, and medication error refer to AEs associated with uses of the study drug outside of that specified by the protocol. Overdose, misuse, abuse, and medication error are defined as follows:

Overdose Accidental or intentional use of the study drug in an amount higher

than the protocol-defined dose

Misuse Intentional and inappropriate use of study drug not in accordance with

the protocol

Abuse Sporadic or persistent intentional excessive use of study drug

accompanied by harmful physical or psychological effects

Medication error Any unintentional event that causes or leads to inappropriate study

drug use or subject harm while the study drug is in the control of site

personnel or the subject.

Eisai Confidential Page 55 of 71

All AEs associated with overdose, misuse, abuse, or medication error should be captured on the CRF and also reported using the procedures detailed in Reporting of Serious Adverse Events (Section 9.5.4.1) even if the AEs do not meet serious criteria. Abuse is always to be captured as an AE. If the AE associated with an overdose, misuse, abuse, or medication error does not meet serious criteria, it must still be reported using the SAE form and in an expedited manner but should be noted as nonserious on the SAE form and the CRF.

9.5.4.3.2 Reporting of Study-Specific Events

The occurrence of T-cell lymphoblastic lymphoma/T-cell acute lymphoblastic leukemia or myeloid malignancy including myelodysplastic syndrome will be considered events of interest for this study. These events should be directly reported to the sponsor as soon as possible (no later than 1 business day) after obtaining the information. In addition, these events should be directly reported to the sponsor or by fax with completed SAE report promptly. The faxed report should be followed up by the original SAE report. Events of interest for this study must be followed to resolution or, if resolution is unlikely, to stabilization. Any event of interest to be related to the study drug or any protocol-required procedure judged by the investigator or subinvestigator should be reported to the sponsor regardless of the length of time that has passed since study completion.

9.5.4.4 Expedited Reporting

The sponsor must inform investigators, the head of the medical institution, and regulatory authorities of reportable events, in compliance with applicable regulatory requirements, on an expedited basis (ie, within specific time frames). For this reason, it is imperative that sites provide complete SAE information in the manner described above.

9.5.4.5 Breaking the Blind

Not applicable.

9.5.4.6 Regulatory Reporting of Adverse Events

Adverse events will be reported by the sponsor to regulatory authorities in compliance with local and regional law and established guidance. The format of these reports will be dictated by the local and regional requirements.

9.5.5 Completion/Discontinuation of Subjects

A subject may elect to discontinue the study at any time for any reason. All subjects who discontinue the study are to complete the study's early discontinuation procedures indicated in the Schedule of Procedures/Assessments (Table 5).

The investigator or subinvestigator will promptly explain to the subject involved that the study will be discontinued for that subject and provide appropriate medical treatment and other necessary measures for the subject. A subject who has ceased to return for visits will be followed up by mail, phone, or other means to gather information such as the reason for

Eisai Confidential Page 56 of 71 FINAL: 29 Jan 2021

Eisai Confidential Page 57 of 167

failure to return, the status of treatment compliance, the presence or absence of AEs, and clinical courses of signs and symptoms.

For subjects who discontinue the study early, 1 primary reason for discontinuation and study disposition information will be collected on the CRF.

9.5.6 Abuse or Diversion of Study Drug

Not applicable.

9.5.7 Confirmation of Medical Care by Another Physician

The investigator, subinvestigator, or clinical research coordinator will instruct subjects to inform site personnel when they are planning to receive medical care by another physician. At each visit, the investigator, subinvestigator, or clinical research coordinator will ask the subject whether he/she has received medical care by another physician since the last visit or is planning to do so in the future. When the subject is going to receive medical care by another physician, the investigator or subinvestigator, with the consent of the subject, will inform the other physician that the subject is participating in the clinical study.

9.6 Data Quality Assurance

This study will be organized, performed, and reported in compliance with the protocol, SOPs, working practice documents, and applicable regulations and guidelines. Site audits will be made periodically by the sponsor's qualified compliance auditing team, which is an independent function from the study team responsible for conduct of the study.

9.6.1 Data Collection

Data required by the protocol will be collected on the CRFs. As defined by GCP, the CRF is a printed, optical, or electronic document designed to record all of the protocol-required information to be reported to the sponsor on each study subject.

Data collection on the CRF must follow the instructions described in the CRF Completion Guidelines. The investigator has ultimate responsibility for the collection and reporting of all clinical data entered on the CRF. The investigator must sign the completed CRF to attest to its accuracy, authenticity, and completeness.

Completed, original CRFs are the sole property of the sponsor and should not be made available in any form to third parties without written permission from the sponsor, except for authorized representatives of the sponsor or appropriate regulatory authorities.

Eisai Confidential Page 57 of 71 FINAL: 29 Jan 2021

Eisai Confidential Page 58 of 167

9.6.2 Clinical Data Management

All software applications used in the collection of data will be properly validated following standard computer system validation that is compliant with all regulatory requirements. All data, both CRF and external data (eg, laboratory data), will be entered into a clinical system.

9.7 Statistical Methods

All statistical analyses will be performed 1) after data cut-off for primary analysis or 2) after the study is completed and the database is locked and released. Data cut-off will be performed at Week 56 (after more than 12 months from the start of treatment to all subjects), or after the discontinuation of treatment before 12 months. Statistical analyses will be performed using SAS software or other validated statistical software as required. Details of the statistical analyses will be included in a separate SAP.

9.7.1 Statistical and Analytical Plans

The statistical analyses of the study data are described in this section. Further details of the analytical plan will be provided in the SAP, which will be finalized before database lock.

9.7.1.1 Study Endpoints

9.7.1.1.1 PRIMARY ENDPOINT

ORR of BOR

9.7.1.1.2 SECONDARY ENDPOINTS

- PFS
- DOR
- TTR
- Safety assessments (AEs, clinical laboratory tests, vital signs, body weight, 12-lead ECGs, ECOG-PS, and physical examinations)

9.7.1.1.3 EXPLORATORY ENDPOINTS

- Concentration of tazemetostat
- Frequency of EZH2 gene mutation

9.7.1.2 Definitions of Analysis Sets

Efficacy Analysis Set will include efficacy evaluable subjects who received at least 1 administration of the study drug and who has at least 1 appropriate tumor assessment data of Screening 2 and post-baseline.

Eisai Confidential Page 58 of 71

Pharmacokinetic Analysis Set will include subjects who received at least 1 administration of the study drug and had at least 1 concentration data of tazemetostat.

Biomarker Analysis Set will include subjects who have conducted EZH2 gene mutation assessment at Screening.

Safety Analysis Set will include subjects who received at least 1 administration of the study drug.

9.7.1.3 Subject Disposition

Subjects who signed informed consent (for tumor EZH2 gene mutation test and study treatment), were registered in the study, and failed screening (Screening 1 and Screening 2) and the reason for screen failures will be presented. Subjects who were treated, were not treated, were ongoing, and discontinued from study treatment and the reason for discontinuation will be presented.

9.7.1.4 Demographic and Other Baseline Characteristics

Demographic and other baseline characteristics for the Safety/Efficacy Analysis Set will be summarized in whole or each disease (cohort). Continuous demographic and baseline variables include age, height, and body weight; categorical variables include sex, age group, race, ethnics, ECOG-PS, diagnosis (including COO, as needed), clinical staging, B symptoms, and prior therapies for primary disease (chemotherapy, radiotherapy, and autologous stem cell transplantation, etc.).

9.7.1.5 Prior and Concomitant Therapy

All investigator terms for medications recorded in the CRF will be coded to an 11-digit code using the World Health Organization Drug Dictionary (WHO DD) preferred name. Prior medications will be defined as medications that stopped before the first dose of study drug. Concomitant medications will be defined as medications that started before the first dose of study drug and were continuing at the time of the first dose of study drug, or started on or after the date of the first dose of study drug up to the final observation. All prior and concomitant medications will be presented in subject data listings.

9.7.1.6 Efficacy Analyses

FINAL: 29 Jan 2021

This analysis will be performed on the Efficacy Analysis Set. All summary of efficacy will be conducted for each disease (cohort).

9.7.1.6.1 PRIMARY EFFICACY ANALYSIS

BOR will be summarized. The rate of subjects whose BOR is CR or PR is calculated as ORR, and its corresponding 2-sided exact 90% confidence intervals (CIs) using the method of Clopper–Pearson will also be calculated. A waterfall plot will be presented for the percent changes from baseline in the sum of the diameters of target lesions at post-baseline nadir.

Eisai Confidential Page 59 of 71

Eisai Confidential Page 60 of 167

9.7.1.6.2 SECONDARY EFFICACY ANALYSES

- Analysis of PFS
 PFS will be summarized by Kaplan-Meier method using median with 95%CI.
- Analysis of DOR DOR will be summarized by Kaplan-Meier method in responders.
- Analysis of TTR
 TTR will be summarized by descriptive statistics in responders.

9.7.1.7 Pharmacokinetic, Pharmacodynamic, Pharmacogenomic, and Other Biomarker Analyses

9.7.1.7.1 PHARMACOKINETIC ANALYSES

This analysis will be performed on the Pharmacokinetic Analysis Set. The plasma concentrations of tazemetostat will be summarized by timepoint.

9.7.1.7.2 PHARMACODYNAMIC, PHARMACOGENOMIC, AND OTHER BIOMARKER ANALYSES

This analysis will be performed on the Biomarker Analysis Set. The rate of the tumor EZH2 gene mutation will be calculated in each disease.

9.7.1.8 Safety Analyses

This analysis will be performed on the Safety Analysis Set in whole or each disease (cohort).

9.7.1.8.1 EXTENT OF EXPOSURE

The number of cycles/days on treatment, quantity of study drug administered, and the number of subjects requiring study drug dose reductions, interruption, and discontinuation will be summarized.

9.7.1.8.2 ADVERSE EVENTS

The AE verbatim descriptions (investigator terms from the CRF) will be classified into standardized medical terminology using the Medical Dictionary for Regulatory Activities (MedDRA). Adverse events will be coded to the MedDRA lower level term (LLT) closest to the verbatim term. The linked MedDRA preferred term (PT) and primary system organ class (SOC) are also captured in the database.

A treatment-emergent adverse event (TEAE) is defined as an AE that emerges during treatment, having been absent at pretreatment (baseline) or

- Reemerges during treatment, having been present at pretreatment (baseline) but stopped before treatment, or
- Worsens in severity during treatment relative to the pretreatment state, when the AE is continuous.

Eisai Confidential Page 60 of 71 FINAL: 29 Jan 2021

Eisai Confidential Page 61 of 167

Only those AEs that are treatment-emergent will be included in summary tables. All AEs, treatment-emergent or otherwise, will be presented in subject data listings.

The number (percentage) of subjects with TEAEs will be summarized by SOC and PT. A subject will be counted only once within an SOC and PT, even if the subject experienced more than 1 TEAE within a specific SOC and PT. The number (percentage) of subjects with TEAEs will also be summarized by highest CTCAE grade.

The number (percentage) of subjects with treatment-related TEAEs will be summarized by SOC and PT. Treatment-related TEAEs include those events considered by the investigator to be related to study treatment. The number (percentage) of subjects with treatment-related TEAEs will also be summarized by highest CTCAE grade.

The number (percentage) of subjects with SAEs and TEAEs leading to death, discontinuation from study drug, study drug dose reduction or interruption will be summarized by SOC and PT. Subject data listings of all SAEs and AEs leading to death, discontinuation from study drug, study drug dose reduction or interruption will be provided.

9.7.1.8.3 LABORATORY VALUES

Laboratory results will be summarized using Système International (SI) units. For all quantitative parameters listed in Section 9.5.1.5.3, the actual value and the change from baseline to each postbaseline visit and to the last observation will be summarized by visit using descriptive statistics. Qualitative parameters will be summarized using frequencies (number and percentage of subjects), and changes from baseline to each postbaseline visit and to the last observation will be reported using shift tables. Percentages will be based on the number of subjects with both nonmissing baseline and relevant postbaseline results.

CTCAE v4.03 will be used to identify subjects with treatment-emergent markedly abnormal laboratory values (TEMAVs). The details of TEMAV definitions will be provided in the SAP. TEMAVs will be summarized for overall visits.

9.7.1.8.4 VITAL SIGNS

Descriptive statistics for vital signs parameters (ie, systolic and diastolic blood pressure, pulse, temperature) and body weight and changes from baseline will be presented by visit.

9.7.1.8.5 ELECTROCARDIOGRAMS

ECG assessments will be performed at each visit. Descriptive statistics for ECG parameters and changes from baseline will be presented by visit.

Shift tables will present changes from baseline in ECG parameters.

In addition, the number (percentage) of subjects with at least 1 postbaseline abnormal ECG result in QTcF will be summarized. Clinically abnormal ECG results in QTcF will be categorized as follows:

Eisai Confidential Page 61 of 71 FINAL: 29 Jan 2021

Eisai Confidential Page 62 of 167

Absolute QTcF interval prolongation:

- QTcF interval >450 msec
- QTcF interval >480 msec
- QTcF interval >500 msec

Change from baseline in QTcF interval:

- QTcF interval increases from baseline >30 msec
- QTcF interval increases from baseline >60 msec

9.7.1.8.6 OTHER SAFETY ANALYSES

ECOG-PS will be summarized by scale at each visit and by highest postbaseline scale.

9.7.2 Determination of Sample Size

In cohort 1, 8 efficacy evaluable FL patients with EZH2 mutation are required to detect lower limit of the 90% CI that exceed the 10% threshold in ORR, which is the primary endpoint of the study, with the expected ORR of 50% with power of approximately 80%.

In cohort 2, 13 efficacy evaluable DLBCL patients with EZH2 mutation are required to detect lower limit of the 90% CI that exceed the 10% threshold in ORR, which is the primary endpoint of the study, with the expected ORR of 40% with power of approximately 80%.

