7.2.4 Diffuse Large B-Cell Lymphoma

DLBCL is a B-cell type of lymphoma that derives from germinal center B-cells and is a diverse set of diseases that have various clinical features, immunophenotypes, genetic and chromosomal abnormalities. DLBCL is classified to germinal center B-cell like (GCB) type and the others (non-GCB type including activated B-cell like type) based on gene expression profile, in approximately a half of proportion respectively (Lenz, et al., 2008). Outside Japan, gain-of-function mutation of EZH2 is reported in 22% of GCB type while no activating mutation of EZH2 is reported in non-GCB type (Morin, et al., 2010). The patient survey by the Ministry of Labor, Health, and Welfare (2014) has reported that approximately 10,000 people are categorized as "international classification of disease C833: large cell (diffuse)". This survey also indicates approximately 38,000 people are categorized as "international classification of disease C859: non-Hodgkin's lymphoma, unspecified type" and some of them are thought to be DLBCL. The proportion of DLBCL subtype in Japan was 45.3% among malignant lymphoma according to the survey of the incidence of malignant lymphoma encoded by classification of disease (Chihara, et al., 2014). Based on the information on Section 7.2.1 Epidemiology of Malignant Lymphoma and these reports, it is estimated that approximately 3,200 people are diagnosed as DLBCL with EZH2 gene mutation and DLBCL with EZH2 gene mutation is prevalent in approximately 1,300 patients per year.

Eisai Confidential Page 22 of 71 FINAL: 29 Jan 2021

Eisai Confidential Page 23 of 167

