7.4.1.4 Summary of Efficacy in Clinical Studies Conducted Outside Japan

As of 01 June 2017, the efficacy of tazemetostat was reported as interim result of ongoing Phase 2 study (Study E7438-G000-101 [n=203]). The ORR (primary endpoint) was 92% (12/13 subjects) in EZH2 gene mutation-positive FL, 26% (14/54 subjects) in EZH2 gene mutation-negative (wild-type) FL, 29% (5/17 subjects) in EZH2 gene mutation-positive DLBCL of germinal center origin subtype, and 15% (18/119 subjects) in EZH2 gene mutation-negative (wild-type) DLBCL of either germinal center origin or non-germinal center origin subtype. Tazemetostat showed high efficacy in subjects with EZH2 gene mutation compared to subjects with wild type (Morschhauser, et al., 2017).

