7.5 Study Rationale

FINAL: 29 Jan 2021

In the Phase 1 part of the Study E7438-G000-101 conducted outside Japan, the recommended Phase 2 dose of tazemetostat has been determined to be 800 mg BID. As interim result of ongoing Phase 2 part of the study, encouraging efficacy of tazemetostat was reported in relapsed or refractory FL and DLBCL with EZH2 gene mutation.

In the Phase 1 study of the Study E7438-J081-106 conducted in Japan, no DLT was observed in tazemetostat 800 mg BID by continuous regimen; therefore, tazemetostat 800 mg BID, which is RP2D outside Japan, was confirmed to be well tolerated in Japanese subjects. Also, the favorable safety profile of tazemetostat has been shown in Japanese and non-Japanese subjects.

Based on above, the Phase 2 study (E7438-J081-206) was planned to evaluate the efficacy and safety of tazemetostat in Japanese patients with relapsed or refractory B-cell NHL (FL and DLBCL) with EZH2 gene mutation.

In this study, tazemetostat 800 mg BID (1600 mg total daily dose) will be administered orally in continuous cycles of 28 days each, and the treatment will continue until disease progression, development of unacceptable toxicity, subject's requests to discontinue, withdrawal of consent, or study termination by the sponsor.

As the patients eligible to this study are extremely few and standard therapy/treatment to prolong the overall survival for relapsed or refractory B-cell NHL has not been established yet, the response itself is considered to be clinically meaningful. Therefore, the primary endpoint of the study was set as ORR, by referring the interim result of ongoing E7438-G000-101 study outside of Japan. Regarding sample size of this study, in cohort 1, 8 efficacy evaluable FL patients with EZH2 mutation are required to detect lower limit of the 90% CI that exceed the 10% threshold in ORR, which is the primary endpoint of the study, with the expected ORR of 50% with power of approximately 80%. In cohort 2, 13 efficacy evaluable DLBCL patients with EZH2 mutation are required to detect lower limit of the 90% CI that exceed the 10% threshold in ORR, which is the primary endpoint of the study, with the expected ORR of 40% with power of approximately 80%.

Eisai Confidential Page 29 of 71

Eisai Confidential Page 30 of 167

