9 INVESTIGATIONAL PLAN

9.1 Overall Study Design and Plan

This is a multicenter, open-label, phase 2 study in relapsed or refractory B-cell NHL patients with EZH2 gene mutation, and consists with 2 cohorts. The study will assess efficacy and safety of tazemetostat in FL patients with EZH2 gene mutation in cohort 1, and DLBCL (including primary mediastinal B-cell lymphoma and transformed FL) patients with EZH2 gene mutation in cohort 2.

Note: As per regulatory requirements in Japan, from the time tazemetostat is approved by the regulatory authority, subjects who meet approved indication of tazemetostat will continue this study as a post-marketing study (clinical study shall be deemed to post-marketing study in this protocol) until tazemetostat is commercially available for individual subjects at each study site. For these subjects, the end of the study will be the date of the last study treatment or evaluation at discontinuation, whichever comes later.

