#### 5.3.3 Multiple Comparisons/Multiplicity

No statistical comparison is planned in this study.

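### Does cohort 2's unsourced 40% response rate call for a stated basis or a power table in the plan?

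*Protocol*

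**What the plan says.** Protocol 9.7.2 states that "13 efficacy evaluable DLBCL patients with EZH2 mutation are required" to obtain a "lower limit of the 90% CI that exceed the 10% threshold in ORR", "with the expected ORR of 40% with power of approximately 80" per cent. The same statement appears in the protocol synopsis, in protocol 7.5 and in SAP 4. None of the four places derives the 40% or shows power at another rate, and protocol 9.7.4 (other statistical issues) is marked not applicable.

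Protocol 9.7.1.6.1 fixes the interval as Clopper–Pearson, two-sided 90%. SAP 5.4.1 adds a 95% interval. SAP 5.3.3 says "No statistical comparison is planned in this study".

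The relevant earlier evidence is in protocol 7.4.1.4, which reports an interim response rate of "29% (5/17 subjects) in EZH2 gene mutation-positive DLBCL of germinal center origin subtype". Protocol 7.5 cites that interim result as the reason for choosing ORR as the primary endpoint. Its next sentence begins "Regarding sample size of this study, in cohort 1, 8 efficacy evaluable FL patients" and goes on to sample size without tying the 40% to that result.

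**The concern.** A reader who looks for the origin of 40% finds only one candidate, and it is more than ten points lower. It is also a close match to much of the cohort. Protocol 7.2.4 notes that "no activating mutation of EZH2 is reported in non-GCB type", so mutation-selected DLBCL should be largely germinal-centre disease, the subtype in which 5/17 was seen. The cohort is somewhat wider, since protocol 9.1 describes it as "DLBCL (including primary mediastinal B-cell lymphoma and transformed FL) patients with EZH2 gene mutation in cohort 2", but the documents give no response rate for either of the added entities.

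With 13 subjects the chance of clearing the threshold depends steeply on the true rate. If 40% was optimistic, the advertised power is overstated, and a miss could reflect the design as much as the drug. The phrase about approximate power does not show this.

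**Working it through.** **Inputs.** n = 13, threshold 10% and expected ORR 40% (protocol 9.7.2); two-sided 90% Clopper–Pearson interval (protocol 9.7.1.6.1); no interim look (protocol 9.7.3); earlier result 5/17 (protocol 7.4.1.4).

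**Step 1: the responder count implied by the criterion.** The lower limit for x responders of n is the 5% quantile of a Beta(x, n − x + 1) distribution.

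- 3/13: 90% interval 6.6% to 49.5%. The lower limit is below 10%.
- 4/13: 90% interval 11.3% to 57.3%. The lower limit is above 10%.

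So at least 4 of 13 are needed. If the true ORR is 10%, P(X ≥ 4) = 3.4%.

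**Step 2: reproduce the plan's figure.** Power = 1 − Σ C(13, x) pˣ (1 − p)¹³⁻ˣ over x = 0 to 3. At p = 0.40 the four terms are 0.0013, 0.0113, 0.0453 and 0.1107. They sum to 0.1686, so power is 83.1%. With 12 subjects the count is still 4 and power is 77.5%. Thirteen is therefore the smallest n that reaches 80%, as the protocol says.

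**Step 3: power at other true rates, n = 13.**

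| True ORR | Power | Chance of fewer than 4 responders |
|---|---|---|
| 40% | 83.1% | 16.9% |
| 38% | 79.2% | 20.8% |
| 35% | 72.2% | 27.8% |
| 30% | 57.9% | 42.1% |
| 5/17 (29.4%) | 56.1% | 43.9% |
| 25% | 41.6% | 58.4% |

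Solving P(X ≥ 4) = 0.80 gives p = 38.4%. The margin below the assumed value is 40 − 38.4 = 1.6 points.

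**Step 4: does 5/17 contradict 40%?** The exact 90% interval for 5/17 is 12.4% to 52.2%, which contains 40%. If the true rate were 40%, 5 or fewer responders of 17 would occur 26% of the time. The earlier data are compatible with 40%, though they do not point to it.

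**Step 5: what designing at 29.4% would have meant.** The smallest n with at least 80% power is 26, twice the planned size. Protocol 7.5 describes eligible patients as very scarce.

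**Step 6: where the 40% is used.** It enters the choice of n and nothing else. The ORR, its intervals, PFS, DOR and TTR are all computed without it, and the 3.4% in step 1 does not depend on it.

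**Step 7: timing.** The synopsis gives 02 Dec 2020 as the imaging cut-off, set at 24 months after the last enrolment, so enrolment ended about December 2018. SAP version 2.0 is dated 31 May 2022.

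**The case for a change.** The best argument for acting is that the remedy costs one or two sentences and the omission is real. The two cohorts also sit oddly together. Cohort 1 assumes 50% where the interim rate was 12/13 (92%), while cohort 2 assumes 40% where it was 29%. One assumption lies well below the sponsor's data and the other above it, and neither is explained. A reader who supposed that both came from the interim result would be misled about cohort 2. At 5/17 the chance of missing the criterion is about 44%, against 17% at 40%, and someone reading a failed cohort would want to know that.

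Part of this stands: no source is documented, and the power is sensitive to the value chosen. The rest does not lead to a change. The comparison with cohort 1 shows that interim rates were not simply copied into either cohort, which points to a general brevity of drafting. The power curve follows from inputs the plan already states. After a miss, the reported interval serves the reader better than a design-stage table: at 3/13, for example, its upper limit is 49.5%, so the reader sees directly that 40% has not been ruled out. Writing a count of 4 responders into the SAP would carry its own risk, because it is tied to the number evaluable. At 15 evaluable subjects the count becomes 5.

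**Conclusion.** No change to the plan. The stated sample size and power are correct for the stated inputs (83.1% exact at 40%, with 13 the smallest sufficient n). The gap is a missing sentence of rationale. Its size can be stated fairly: 80% power holds only down to a true ORR of about 38.4%, and power is 56% to 58% if the truth is near 29% to 30%. That affects how optimistic the design looks in hindsight. It does not affect the validity of any estimate or interval, and with enrolment long finished it cannot affect n. The sponsor may choose to say in the clinical study report where 40% came from, or that no source was recorded, but nothing depends on it.

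This rests on exactly 13 evaluable subjects, the Clopper–Pearson 90% interval, and the 5/17 result as the only response rate the documents give for EZH2-mutant DLBCL.
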